Aim 1: The primary outcome measure is the rate of severe maternal outcome (SMO). This is a composite measure drawn from WHO near miss morbidity criteria (Table 2). Secondary outcome measures include: the maternal mortality rate, maternal near miss rate and case fatality rates for postpartum hemorrhage, hypertensive disease and sepsis – the three most common causes of maternal death. The event rates for both primary and secondary outcomes will be compared using logistic regression models with the Generalized Estimating Equations approach to take into account of patients within clustering (due to time blocks). Exploratory analyses will be used to determine if a) the intervention is more powerful in certain subgroups of women and b) if any provider was consistently different in maternal outcomes regardless of intervention. The interaction between study arm and comorbidities (HIV, hypertension, pulmonary, cardiac or kidney disease, malaria) or provider will be tested in the logistic regression models. Subgroup effects will be reported if there is strong evidence of heterogeneity of intervention effect

Aim 2: We will apply the RE-AIM model to conduct a quantitative evaluation of the implementation of the intervention used in Aim. Table 4 describes the primary metrics to be measured and data sources from which it will be collected.

RE-AIM Implementation Science Framework ^{37,38}			
Metric	Dimension	Study Measure	Data source
Reach	Proportion of target population that participated in the intervention	
 Percent of women with successful placement of biosensor after delivery Total length of time for monitoring over 24hrs postpartum Percent of women participating in monitoring for 24 hrs 	
 Physiologic data from biosensor Time of delivery from chart records & theatre log books
Efficacy	Success rate if implemented as in guidelines	
 Percent of women with HR, BP, RR and Tp available at least every 4 hours for 24 hrs after delivery Percent of appropriate SMS alerts sent 	
 Physiologic data from biosensor RA review of mobile phones for SMS alerts and time of receipt

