On average approximately 8-10 emergency cesarean deliveries are performed at MRRH daily. Thus, in a two week block we estimate ~ 112 emergency cesareans performed. We plan to capture all women delivered by emergency cesarean during an intervention block thus minimizing the risk of selection bias based on the severity level. Assuming 85% of women consent to participation (conservative estimate based on >90% recruitment in prior studies)^{5,74,75}, this yields an estimated 95 women per block. Over 12 months of enrollment, we will therefore have 13 intervention blocks and 13 control blocks. This yields an estimated 1,235 women in the intervention group and 1,235 in the control group. Assuming an intraclass correlation coefficient of 0.01, the effective sample size after taking account of clustering is 633 per group. This will allow us to detect a difference of 5.7% in the SMO rate between the two study arms, with a two-sided significance level of 0.05, and 80% power, assuming a baseline rate of SMO of 13% ^{71,73}

Risk/Discomforts and protections

Clinicians:

- Risk of false alerts, alert fatigue: Clinicians will be asked to hold a mobile phone and respond to alerts. It is possible that alerts of physiologic sign abnormalities may not correspond to a developing or established clinical abnormality and in responding to the alert clinicians may become fatigued from alerts. Study investigators will monitor for this occurrence and the impact on clinician performance and duties and adjust study protocols as necessary
- Risk of diversion and interruptions to work on other patients: Alerts sent to clinicians may also prompt them to perform additional exams or clinical procedures that may or may not be beneficial to the patients from which alerts were received. This may divert attention or human resource away from other clinical needs. We will monitor for any diversions resulting in substandard clinical care. If these occur we will consider protocol modifications. Any safety concerns or adverse events arising because of false alerts or diversions will be communicated to the IRB within 10 days.

Peripartum women:

- Theoretical risk of exposure to radio emissions from Wi-Fi from the biosensor: There is a theoretical risk of exposure to Wi-Fi signals from the biosensor worn by women participating in

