#### Test size and confidence levels

Analyses, including the primary analysis, will be based on two-sided  $\alpha=0.05$  level tests and 95% confidence intervals (CIs). No adjustment will be made for multiple comparisons.

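### The protocol asks whether any provider's outcomes differ in both arms alike, but the only provider test it names, the arm-by-provider interaction, does not answer that

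*Protocol*

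**What the plan says.** Protocol, Biostatistical Analysis, Aim 1, poses two exploratory questions: (a) whether the intervention works better in some subgroups of women, and (b) "if any provider was consistently different in maternal outcomes regardless of intervention". The sentence that follows opens with "The interaction between study arm and comorbidities", lists the comorbidities, and ends "or provider will be tested in the logistic regression models". The reporting rule is "Subgroup effects will be reported if there is strong evidence of heterogeneity of intervention effect". The Aim 1 comparison itself uses "logistic regression models with the Generalized Estimating Equations approach", with time blocks as the clusters.

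Under Aim 2 the protocol also makes comparisons by provider, but only of the RE-AIM implementation measures, not of maternal outcomes.

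The SAP section on Aim 1 keeps the subgroup and comorbidity interactions. It mentions neither question (b) nor any provider term, and its random effect is for time block only. On multiplicity the SAP says "No adjustment will be made for multiple comparisons".

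**The concern.** Question (b) is about a provider whose outcomes are better or worse whichever arm the woman is in. That is a main effect of provider. The named test has a different null hypothesis, that the intervention effect is the same for every provider. A provider with uniformly worse outcomes satisfies that null. Conversely, the null fails when providers have similar outcomes on average but the intervention works better under some than others. The test and its reporting rule therefore fit question (a), effect modification, and not question (b).

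At stake is one exploratory answer that the protocol promises. The primary and secondary comparisons do not depend on it.

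**Working it through.** **Inputs from the documents.** Protocol, Sample Size: 13 intervention and 13 control blocks, 95 women per block, 1,235 women per arm, ICC 0.01, effective size 633 per arm, control SMO rate 13%, difference 5.7 points, "with a two-sided significance level of 0.05, and 80% power". Protocol, Methodology (Setting): 13 consultants/specialists, 39 postgraduate doctors and 40 midwives. The protocol does not say which group counts as the provider.

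**Assumptions not in the documents.** 2, 5, 13 or 40 providers, with women spread evenly over them; provider effects with SD 0 to 0.8 on the log-odds scale, or one outlying provider with odds ratio 2 or 3; a block SD of 0.18 on the log-odds scale in the GEE runs.

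**The plan's own figure.** None is given for the provider analysis. The sample-size figure, which supplies the inputs, reproduces:
- Design effect 1 + 95 × 0.01 = 1.95, and 1,235 / 1.95 = 633.3 (with 94 in place of 95: 1.94 and 636.6).
- At 633 per arm, 13% against 13 + 5.7 = 18.7% has 79.4% power, in line with the stated 80%. For a fall to 13 − 5.7 = 7.3%, power is 92.0%.

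**Why the interaction is blind to (b).** Let logit(p) = α + β·arm + u_k for provider k. The interaction contrast between providers k and 1 is [(α + β + u_k) − (α + u_k)] − [(α + β + u_1) − (α + u_1)] = β − β = 0, whatever the u_k.

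In numbers, 13% and 7.3% are odds of 0.1494 and 0.0787, an arm odds ratio of 0.527. A provider with odds ratio 2 in both arms has odds of 0.2989 and 0.1575, that is 23.0% and 13.6%. The arm odds ratio is again 0.527.

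**Simulation 1: likelihood-ratio tests, 1,235 per arm, no block clustering, 2,000 replicates.** Where one figure stands in brackets, the first is for no arm effect and the bracketed one for 13% against 7.3%. Ranges cover both.

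| Providers | True differences, equal in both arms | Interaction rejects | Main effect rejects |
|---|---|---|---|
| 5 | none | 4.9-5.8% | |
| 5 | SD 0.3 to 0.8 | 4.2-5.8% | SD 0.3: 81% (74%); SD 0.5: 96% (93%) |
| 13 | none | 5.2-6.0% | |
| 13 | SD 0.3 to 0.8 | 5.9-7.3% | SD 0.3: 85% (75%); SD 0.5: 99% (99%) |
| 13 | one provider, OR 2 | 6.5% (6.2%) | 62% (55%) |
| 13 | one provider, OR 3 | 6.2% (6.0%) | 99% (97%) |
| 40 | none | 12.3% (17.3%) | 6.0% (8.1%) |
| 40 | SD 0.5 | 14.0% (15.1%) | 99.9% (99.0%) |

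**Simulation 2: nearer the planned model.** 26 blocks of 95, independence GEE, block-robust Wald tests, 600 replicates. Ranges cover both arm effects.

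| Providers | Interaction, no differences | Interaction, SD 0.5 | Main effect, no differences | Main effect, SD 0.5 |
|---|---|---|---|---|
| 2 | 6.5-7.0% | 6.5-6.7% | 6.0-6.5% | 71.2-75.2% |
| 5 | 12.8-15.7% | 14.2-14.5% | 11.2-16.0% | 94.7-96.5% |
| 13 | 57.5-58.5% | 57.8-64.8% | 52.8-56.5% | 100% |

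The interaction test stays near its own null rate; the largest shift is from 57.5% to 64.8%. With many provider terms and only 26 blocks that null rate is far above 5%, and the same holds for the block-robust main-effect test.

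**Scale.** Let provider differences instead be constant on the risk scale (5 providers spread over plus or minus 4 points, no block variation). With 13% against 7.3% by arm, the interaction rejects 10.5% with model-based and 25.5% with block-robust tests, against 99% for the block-robust main effect. With no arm effect the interaction figures are 5.3% and 12.2%.

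**The case against.** Several points can fairly be made for the plan.

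- *The interaction bears on consistency.* It checks whether a provider difference is the same in both arms, and the model that contains it would normally contain provider terms too. This stands, and it makes the remedy small. But the plan neither tests nor reports those terms, and absence of interaction does not show that any provider differs.
- *The sentence could mean that provider itself is tested.* This parse is possible but strained. The grammar and the reporting rule both point to the interaction. If a main effect was meant, the sentence still needs rewording.
- *The analysis is exploratory and absent from the SAP.* This stands and limits the weight of the point. If the SAP governs, the test will not be run, and what remains is an unanswered protocol question and a disagreement between the two documents.

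A reader might go further than the documents allow in four ways.

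- That the trial will report no provider difference when there is one. Nothing says that a non-significant interaction will be read as equal providers. Under block-robust GEE with 13 providers, the test would reject more often than not in any case.
- That a significant interaction will be read as a consistently different provider. The reporting rule ties it to variation in the intervention effect, which is the correct reading.
- That the likelihood-ratio contrast of about 6% against 99% with 13 providers describes the planned analysis. It leaves out block clustering, which the protocol's model includes.
- That the interaction can never respond to consistent differences. This holds on the log-odds scale, the scale of the planned model, but not fully on the risk scale.

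**Conclusion.** The protocol is wrong as written on this point, in a minor and exploratory matter: it pairs a provider main-effect question with an interaction test.

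For provider differences constant on the log-odds scale, the interaction test rejects at about its null rate whatever their size. That is about 4-7% by likelihood ratio with 5 to 13 providers. By block-robust GEE Wald test it is about 13-16% with 5 providers and 58% with 13, with little change when providers differ. A main-effect likelihood-ratio test, ignoring block clustering, rejects about 93-99% at SD 0.5. Neither outcome of the interaction test answers (b).

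The algebra needs no assumption beyond the log-odds scale. The percentages rest on assumed provider numbers and effect sizes, because the documents define neither the provider nor the spread between providers. The documents do not support any inference that the primary or secondary results are affected, or that a particular misreport will follow.

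**What to change.** In the protocol's Aim 1 analysis, answer (b) by testing and reporting the provider main effect in the Aim 1 model that accounts for block. Use a random provider intercept, reported with the individual provider estimates and intervals, or fixed provider terms if providers are few. With many providers, do not rely on a block-robust Wald test of fixed terms: with 13 providers and no true difference it rejected 52.8-56.5% of the time. Keep the arm-by-provider term only for the separate question of whether the intervention effect varies by provider.

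Carry this into the SAP section on Aim 1. Alternatively, drop (b) from the protocol so that the two documents agree.

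The cost is a short text change and one extra exploratory model, with no further patients or procedures. Like the planned test, it needs the provider to be defined and recorded for women in both arms. Protocol, Study Procedures, item 5 uses duty schedules to identify clinicians in intervention blocks, and item 12 does not list the provider among the data extracted. Appendix 1, the chart-review form, was not available to check.

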7. To evaluate if motion in the early post-operative period is related to functionality, mobility and wellness during recovery from cesarean delivery and how recovery relates to financial risks after cesarean delivery.

Methodology

Setting: The research will be carried out in the Department of OB/GYN MRRH in Mbarara, Uganda. This facility is the primary referral hospital in southwest Uganda. It performs ~ 10,000 deliveries per year (~ 30/day), has a maternal mortality ratio of 460 per 100,000 live births (~50-60 deaths per year)

and a cesarean delivery rate of 40%. All women delivered by cesarean are followed and monitored by postgraduate doctors with assistance from midwives. In this facility, postgraduate doctors complete medical training including a two-year internship and practice independently for several years prior to postgraduate training in OB/GYN. Consultant/Specialist OB/GYN supervisors oversee clinical care from home or in-hospital depending on clinical acuity. There are currently 13 consultants/specialists, 39 postgraduate doctors in the institution, and 40 midwives with clinical privileges in the department. The physician to patient ratio ranges from 1:8 during the day to 1:25 during the night and weekends.

Study Population:

The following types of participants will be recruited for study purposes:

- 1) Clinicians: Consultants/Specialists and nurse/midwives with clinical duty on the maternity ward at MRRH during the study period.
- 2) Peripartum women delivered by emergency cesarean during the study period.

Study Intervention:

The intervention in this study is the use of a wireless monitor to perform physiologic monitoring of women undergoing emergency cesarean delivery for the first 24 hours after completion of the cesarean.

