Cardiopulmonary resuscitation	Emergency procedures including chest compressions and lung ventilation.

12. The research assistant will also extract data on (age, district of origin, education level, occupation, referred in from another facility), obstetric history (parity, gestational age at delivery, antenatal complications) and medical comorbidities (HIV, chronic hypertension, cardiac, pulmonary or kidney disease). Information on timing of delivery, indication for cesarean

delivery and decision to incision time for emergency caesarean delivery, documentation of physiologic signs will also be extracted. *See Appendix 1 – Chart Review*

13. At the end of each clinical duty or shift enrolled midwives and specialist doctors will be asked to complete a brief questionnaire which will be administered via electronic survey using redcap survey on the responder phone. This will be to assess if the midwife received any alerts, how they responded and if it influenced clinical management. *See Appendix 2 – Call Duty Follow up Questionnaire. This is estimated to take ~5-10mins to complete.*

14. Up to 30 enrolled clinicians who participated in the monitoring system will also be approached at a convenient time for a in depth interview. We will also approach other key stakeholders including clinicians in leadership positions who may not have participated in the monitoring system. These interviews are intended to gather qualitative data on the facilitators and barriers to use and uptake of the monitoring system. Purposively sampling will be used to approach midwives with high use of the system and low use of the system. *See Appendix 3 – Clinician Interview guide.* Interviews will occur in a private room. Interviews will occur at a time convenient to clinicians (within one week of interaction or observation with the wireless monitoring system) so as not to interrupt clinical care. A digital recorder will be used to record interviews and the trained research assistant will then transcribe and translate interviews administered to clinician and post-partum women participants.

15. During the study period approximately 20 of the enrolled midwives will be observed using the wireless monitoring system to determine time performed to perform the steps for initiating monitoring for a woman. *See Appendix 5 – Time Tracking Form.*

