21. The research assistant will also document any external factors that may affect monitoring every 24 hours e.g. electricity outages or cellular network disruptions, and stock outs

22. After discharge, all patients who completed at least 12 hours of monitoring will receive an invitation to complete a short mobile phone survey to measure functionality, mobility, and wellness at day 1, and at 2,4,6 and 12 weeks post discharge (Appendix 16). At 6 weeks post discharge they will also receive survey assessing for health expenditure, depression and postpartum complications (Appendix 17). The questionnaire will be administered by an automated mobile phone survey system , that allows the participants to receive a prerecorded voice call with the survey and instructs them on answer choices. This will be administered through Engage Spark. EngageSPARK is a social enterprise that offers a browser-based, cloud-hosted platform used to launch interactive Voice IVR and SMS text message campaigns globally. This platform has previously been used in studies of providing airtime incentives to survey participants in Uganda as well as Bangladesh and Colombia. A research assistant will call participants to administer the survey for participants unable to access or complete automated phone surveys. Up to 5 attempts will be made to reach the participant to complete the survey. Participants will receive instruction from a RA on the automated survey at the time of their baseline/acceptability interview conducted as part of the parent study (study procedure #16)

23. At 12 weeks post discharge a research assistant will call participants to administer the last set of surveys as well as an acceptability questionnaire on the use of automated surveys to collect patient reported outcome measures (PROMS) (Appendix 17). Up to 5 attempts will be made to research participants for the survey at these time points.

Table 3: Survey administration timeline

	Day after discharge	2 weeks post discharge	4 weeks post discharge	6 weeks post discharge	12 weeks post discharge
Mobility survey	x	x	x	x	x
Financial Survey				x	x
General Survey				x	x
EPDS				x	x
Acceptability Survey				x	x

Biostatistical Analysis

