Aim 6: From the QUIC scale two scores are calculated: 1) the Informed Consent Aggregate Score (ICAS) and 2) the Therapeutic Misconception Aggregate Score (TMAS). ICAS assesses the quality of consent, ranging from 0-10 (10 is a perfect score) and TMAS assesses the presence of a therapeutic misconception (TMAS), ranging from 0-5 (5 is a perfect score). The ICAS and TMAS scores will be calculated and the means and standard deviations summarized for all participants. We will also summarize individual questions to understand the quality of specific elements of informed consent process. We will compare ICAS and TMAS between women in different stages of labor using one-way ANOVA, and with different pain scores using Spearman correlation and linear regression. Multiple

linear regression will be used to assess the independent association of covariates of interest (demographics, stage of labor, pain score, anxiety, obstetric history and trust) with ICAS and TMAS scores.

Aim 7: Using the motion metric on the wireless device we will summarize mobility in the first 24 hours after their cesarean both as a continuous variable ,and categorizing women into those with low and high mobility. We will summarize the functional status of women in the post discharge period according to the five dimensions measured by the mobility survey : (ability to move independently, ability to selfcare, ability to perform usual activities, level of energy, and overall health, as well as a composite variable with scores of 1-4. 1 being poorest functional status and 4 being better functional status) We will describe functionality at the different time points after discharge using frequency and percent. We will compare return to functionality at the different time points by mobility category in the first 24 hours using regression modelling. We will also describe the rates of impoverishing and catastrophic expenditure after surgery. Summary statistics will be calculated for all expense types. We will compare impoverishing and catastrophic expenditure rates between women with different functional status and early mobility.

Sample Size:

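### The Aim 7 recovery regression uses a low/high mobility split with no stated cut point, although a continuous motion measure is already to be derived

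*Protocol*

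**What the plan says.** The protocol's Specific Aims state the seventh aim as a question of association: "To evaluate if motion in the early post-operative period is related to functionality, mobility and wellness during recovery from cesarean delivery". Under Biostatistical Analysis, Aim 7, motion from the wireless device in the first 24 hours is to be summarised "both as a continuous variable ,and categorizing women into those with low and high mobility".

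The recovery analysis then takes up only the second form: "We will compare return to functionality at the different time points by mobility category in the first 24 hours using regression modelling". The outcome is five dimensions of function "as well as a composite variable with scores of 1-4. 1 being poorest functional status and 4 being better functional status". A separate comparison of financial outcomes leaves the form of the exposure open: "We will compare impoverishing and catastrophic expenditure rates between women with different functional status and early mobility".

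Study Procedures, item 22, sets the population: "all patients who completed at least 12 hours of monitoring will receive an invitation to complete a short mobile phone survey". Only women in intervention blocks are monitored, so the planned intervention group of 1,235 (Sample Size) is the upper bound. The number of survey responders is not given.

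No cut between low and high mobility, and no rule for choosing one, appears in either document. The SAP's Study Objectives and Summary lists Aims 1 to 3 only, so it does not fill the gap.

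**The concern.** A two-group split treats all women on one side of the cut as alike and women just either side of it as different. When the continuous value is already in the dataset, that gives up precision for no gain in data quality, on the question Aim 7 exists to answer.

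The missing cut adds a second weakness. The size and significance of the low/high contrast depend on where the line is drawn, and a reader of the results could not tell whether the line was set before or after the outcomes were seen. There are also five dimensions plus a composite, at the five survey times in Table 3. That makes 6 x 5 = 30 outcome-by-time combinations to which a favourable cut could be matched.

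The same section handles a similar question differently. Aim 6 relates consent scores to pain scores by rank correlation and linear regression, without grouping the pain score.

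**Working it through.** The documents give no sample size, power, effect size, motion distribution or cut for Aim 7, so there is no planned figure to reproduce. The check asks how much a split could cost under stated assumptions.

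**Information lost.** Let X be the motion metric and G the indicator that X exceeds the cut. If the outcome depends linearly on X and the effect is modest, the information kept by using G instead of X is the squared correlation of X and G. For a normal X cut at quantile q, with z_q the standard normal quantile and phi the normal density:

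kept = phi(z_q)^2 / [q(1 - q)]

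- q = 0.50: kept = 2/pi = 0.637, lost 36.3%
- q = 0.33: kept 0.593, lost 40.7%
- q = 0.25: kept 0.539, lost 46.1%
- q = 0.20: kept 0.490, lost 51.0%

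At the upper bound of 1,235 women, a median split of a normal metric leaves the information of 1,235 x 0.637 = about 786. For power, a two-sided 5% test with 80% power has a standardised effect of 1.960 + 0.842 = 2.802. After the split this becomes 2.802 x sqrt(0.637) = 2.235, and power is the normal probability below 2.235 - 1.960 = 0.275, about 61%. The percentage loss does not depend on the number of women.

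**Other shapes.** The squared correlation was simulated with 1,000,000 draws per shape. Percentage of information lost:

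| Shape of metric (assumed) | Cut at median | Cut at 25th percentile | Cut at 75th percentile |
|---|---|---|---|
| Two well-separated groups | 19 | 48 | 48 |
| Uniform | 25 | 44 | 44 |
| Normal | 36 | 46 | 46 |
| Lognormal, sigma 0.5 | 48 | 68 | 39 |
| Laplace | 50 | 52 | 52 |
| Exponential | 52 | 75 | 36 |
| Lognormal, sigma 1 | 73 | 87 | 56 |

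Every shape shows a loss. The size depends on features that the documents do not give.

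**Choice of cut.** With 1,235 women, no true association and 4,000 simulated trials at a nominal 5%, reporting the cut with the smallest p-value gives these false-positive rates:

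- one fixed cut: 5.4%
- best of three: about 12%
- best of nine deciles: 25%
- best of the 81 percentiles from 10 to 90: 39%

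These rates show what an open cut permits. They do not describe anything the protocol says will be done.

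**The case against.** **No single loss can be quoted.** A reader might infer that the plan throws away about a third of the information. That needs a median split, a near-normal metric and a linear effect, and the documents state none of them. Nor can one say that any uneven cut is worse than the median: for the skewed shapes above, a cut at the 75th percentile loses less. This objection stands, and the loss should be given only as a range with its assumptions. If the true relation were a step exactly at the chosen cut, the split would lose nothing and a straight-line term would be the weaker model. That is why a check for non-linearity is needed.

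**No data-driven cut is planned.** The protocol does not say when the cut will be set; it could still be fixed in advance. The survey appendices were not supplied, so a definition there cannot be ruled out. This also stands.

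**Confounding by severity.** A reader might go further and say that the comparison is unadjusted, so that low motion merely marks sicker women. The protocol says only that regression will be used. It names no covariates for Aim 7, unlike Aim 6, but silence is not a plan to omit them. Candidate variables are already in the chart extract (Study Procedures, item 12: "Information on timing of delivery, indication for cesarean" and others).

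Any size put on this bias rests on assumed inputs. Suppose 13% of women have a severe maternal outcome (SMO), 80% of them fall in the low half, and poor function is 60% with SMO against 25% without. With no motion effect, the halves would differ by 0.13 x (0.8 - 0.2)/0.5 x 0.35 = 5.5 points. With 5% SMO the gap is 2.1 points; with 13% SMO but only 60% in the low half it is 1.8. The 13% is the planning rate for the whole trial, whereas Aim 7 surveys only discharged women with at least 12 hours of monitoring, whose rate may be lower. The example shows a direction and cannot support a figure.

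**Limited consequence.** Aim 7 carries no power claim and does not enter the SMO comparison. A continuous summary is already planned. This stands and limits the importance of the point, but it does not change which form of the exposure the recovery regression is said to use.

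**Conclusion.** The point holds in a limited form. The recovery regression is described only by mobility category, a continuous measure of the same exposure will exist, and no cut or cut rule is given in the documents supplied. Assuming a linear effect, the split loses about 36% of the information for a normal metric cut at its median, and 19% to 73% across median splits of the other shapes tried. The open cut leaves room for a choice that would inflate false positives; the documents neither plan that nor exclude it.

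This is a minor, low-cost improvement to an ancillary aim. The primary comparison of SMO rates and the trial's main conclusion are unaffected.

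**What to change.** Amend the Aim 7 analysis text in the protocol, or add a short Aim 7 section to the SAP, as follows:

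- Make the continuous motion metric the exposure in the recovery regression, with a spline or quadratic term to check for non-linearity.
- Keep low/high mobility as a descriptive display, and fix the cut, or the rule for setting it, before motion data are linked to outcomes.
- State which form of early mobility the expenditure comparison uses.

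Two sensitivity analyses are optional: adjustment for chart variables already extracted (timing of delivery, indication, comorbidity, referral), and a rerun excluding women with an SMO in the first 24 hours. The rerun addresses severity more directly, because those chart variables do not themselves measure SMO.

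The cost is a few lines of text, minor extra analysis and a less simple presentation than a two-group table. No new data are needed.
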